Subjects will be recruited from the outpatient clinics of the University of Miami and Jackson Health affiliated clinics. Treating providers must have provided permission to include their patients into the study. The treating physician will identify the potential subject by screening through the clinic records or during the clinic visit. The study will be first introduced to potentially eligible patients by their treating physicians. After the treating physician speaks to the patient and if the patient agrees to be part of the study, the treating physician will refer the patient to the study team via verbal contact, phone contact, secure email or HER message. A member of study team will then speak with the patient and explain the study. This will take place either during the patient's clinic visit or over the phone. If the patient remains interested, patient chart will be accessed to screen for inclusion / exclusion criteria. If the patient qualifies for the study, a copy of the informed consent will be given or mailed. The patients will be encouraged to discuss participation with their primary care providers. They will be asked to call back if they have any questions. The consent

form will be signed at the time of first study visit that would often coincide with the patient's clinic visit.

Study Timelines

Patients will be recruited over a period of one year, 09/01/2018 – 8/31/2022.

All patients will be followed for a period of 6 month. The estimated date to complete the primary analysis will be 06/2023.

8) Study Endpoints*

Primary endpoint: Hemoglobin A1c (HbA1c) at 6 months after enrollment.

Secondary endpoint: 1. Average blood glucose levels (BG) during the study, 2. Incidence of hypoglycemia defined as any reported BG <70 mg/dl, 3. Incidence of severe hypoglycemia defined as any BG <54 mg/dl or patient requiring assistance to recover from hypoglycemia.

9) Procedures Involved*

Subject Enrollment

Subjects will be recruited from the outpatient clinics of the University of Miami and Jackson Health ACC clinics. Treating providers will inform the patients about the study. If a patient shows interest in participation, the study staff will review patient's chart for inclusion / exclusion criteria and provide the patient with more information about the study. Those, eligible for study and willing to participate, will have to provide a written informed consent.

Study Plan

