Baseline characteristics will be summarized and compared to assure that the randomization algorithm resulted in comparable groups. Distributions will be evaluated and transformations to approximate normality will be considered if skewed. The main analysis will be an independent sample t-test or an analysis of covariance to allow for the inclusion of possible covariates such as age, baseline A1C, duration of diabetes, oral anti-diabetic medication use at baseline and number of comorbidities. 95% two-sided confidence interval (calculated on the basis of t-test or analysis of covariance) for the difference between BI and MSI treatment will be used for interpreting the results with regard to the non-inferiority margin. The main outcome variable will be the HbA1c after 6 months of treatment. Secondary outcomes will include mean glucose levels, hypoglycemic events, quality of life measures, patient satisfaction, and treatment failure.

The power calculation is based on the assumption that BI regimen will be non-inferior to MSI regimen for glycemic control. We anticipate that mean HbA1c in the control group (MSI group) at the end of treatment period will be 8.0% with standard deviation of 0.9. The study is designed to demonstrate a non-inferiority margin of 0.5, which is well within the margin of clinical relevance for this population. Group sample sizes of 18 in each group will achieve 95% power to detect non-inferiority using a two-sided, two-sample t-test with alpha 5%. Assuming a 20% drop-out rate, we plan to enroll 44 subjects into this study.

12) Provisions to Monitor the Data to Ensure the Safety of Subjects*

Follow-up and Laboratory test

Patients will be required to send their BG data to the study team every 3 days while the insulin doses are being adjusted and then every 1-2 weeks. Communication will be arranged via secure patient portal emails, telephone or clinic visits. HbA1C will be obtained at randomization and every 3 months after enrollment into the study.

13) Withdrawal of Subjects*

Subject withdrawal criteria

- Patient with severe hypoglycemia needing assistance or BG below 54 ng/dl after two insulin dose adjustments.
- Patient who develops hyperosmolar hyperglycemic syndrome.
- Patient with uncontrolled hyperglycemia >400 despite two insulin dose adjustments.
- Pregnancy during the study

14) Risks to Subjects*

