A relatively large dose of insulin glargine given in the morning may increase the risk of hypoglycemia. We will monitor patients closely and decrease the insulin dose as needed to prevent hypoglycemia. Any severe hypoglycemia in the BI group after two dose adjustments will lead to withdrawal from the study and conversion of insulin regimen to MSI.

There is also a risk of less tight glycemic control in the BI group as compared to the MSI group. However, a relatively high HbA1c is unlikely to cause any harm within the study period. Patients unable to achieve a lower HbA1c as compared to the baseline within first 3 months of the study will be withdrawn from the BI group and placed on MSI regimen.

15) Potential Benefits to Subjects*

Glucose control is likely to improve in all patients participating in this study. The main research intervention in this study will be decreasing the number of insulin injection to once daily instead of multiple daily injections. The remaining outpatient care for diabetes will be as per the ADA guidelines. Knowledge gained from this study may help simplify treatment of diabetes for the elderly patients with T2DM

16) Vulnerable Populations*

Children, incarcerated people and individuals with impaired decision-making capacity will be excluded from participating in the study. The study includes only the patients aged >65 years. Therefore, women of childbearing potential are excluded from this study. In spite of this, if a woman becomes pregnant, she will be immediately excluded from the study. However, we will follow them during the pregnancy for any potential complications that may be related to the study. Students and employees of the University of Miami are eligible for the study. Before they agree to participate, the students will be explained that their decision not to participate or to withdraw from the study will not affect their grades. Employees of the University of Miami will be explained that their decision not to participate or to withdraw from the study will not affect their employment at the University of Miami

17) Sharing of Results with Subjects*

The results of the study will be published in a peer review journal. If the results show that the BI group has significantly better outcomes, patients in the MSI group will be informed and given the option of change in their insulin regimen.

18) Setting

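### Exits for severe hypoglycemia or extreme hyperglycemia carry no provision for later HbA1c or glucose data, so primary-endpoint values can be lost for reasons tied to glucose control

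*Combined protocol and SAP*

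**What the plan says.** All references are to the combined protocol and SAP.

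- **Section 14 (Risks to Subjects), BI arm only:** "Any severe hypoglycemia in the BI group after two dose adjustments will lead to withdrawal from the study and conversion of insulin regimen to MSI".
- **Section 13 (Withdrawal of Subjects), not limited by arm:** "Patient with severe hypoglycemia needing assistance or BG below 54 ng/dl after two insulin dose adjustments" (the unit is evidently meant as mg/dl); "Patient who develops hyperosmolar hyperglycemic syndrome"; "Patient with uncontrolled hyperglycemia >400 despite two insulin dose adjustments". Pregnancy is the fourth criterion. The section does not say whether the patient leaves the study or only the assigned regimen.
- **Section 14, next paragraph:** BI patients whose HbA1c is not below baseline within the first 3 months "will be withdrawn from the BI group and placed on MSI regimen".
- **Section 7 (Study Timelines):** "All patients will be followed for a period of 6 month".
- **Section 12:** "HbA1C will be obtained at randomization and every 3 months after enrollment into the study". BG data are sent every 3 days during dose adjustment and every 1-2 weeks after that.
- **Section 16, on a patient who becomes pregnant:** "However, we will follow them during the pregnancy for any potential complications that may be related to the study".

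Section 8 makes month-6 HbA1c the primary endpoint. The secondary endpoints are average BG, incidence of any BG below 70 mg/dl, and incidence of any BG below 54 mg/dl or need for assistance. Section 11 adds treatment failure as a secondary outcome without defining it, and gives no analysis set and no rule for missing data.

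**The concern.** The exits are triggered by glucose results, which is what the trial measures. If a patient leaves the study at that moment, the missing month-6 HbA1c is missing because of glycemic control and not by chance. A t-test or ANCOVA on the patients who remain then compares groups that are no longer the randomized ones.

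The primary claim is non-inferiority on month-6 HbA1c with a margin of 0.5 points and 22 patients per arm, so a few selective losses can matter. The 20% drop-out allowance protects the number of patients analysed. It does not protect comparability when the losses depend on outcome.

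Converting a BI patient to multiple injections (MSI) after repeated severe hypoglycemia is a sound safety choice and is not disputed. The point concerns only the end of measurement.

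**Working it through.** **1. What each exit rule says.**

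| Exit | Arm | What the patient leaves | Later HbA1c or BG |
|---|---|---|---|
| Severe hypoglycemia after two adjustments (Section 14) | BI | The study, in so many words | Not provided for |
| Same event (Section 13) | Both | Not stated; study is the likely reading | Not provided for |
| Hyperosmolar syndrome; BG above 400 (Section 13) | Both | Not stated; study is the likely reading | Not provided for |
| No HbA1c reduction by 3 months (Section 14) | BI | The BI group only | Reads as a regimen switch within the study |
| Pregnancy (Sections 13 and 16) | Both | The study | Pregnancy complications only |

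Two features support the likely reading of Section 13. Its title concerns withdrawal of subjects, and Section 14 names the study when it treats the same hypoglycemia event. Section 14 also uses different words for the 3-month rule in the very next paragraph, so the document has separate language for a regimen switch.

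**2. What is lost at each exit.**

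- *Hypoglycemia exit:* both Section 8 hypoglycemia endpoints ask whether any event occurred, and this patient has already met them. Later average BG and month-6 HbA1c are lost. Later events are lost too, if the hypoglycemic events in Section 11 are analysed as counts or rates.
- *Hyperglycemia exit:* later average BG, month-6 HbA1c and any later hypoglycemia are lost.
- Treatment failure, once defined, could record that an exit happened, but not the glucose values after it.

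**3. Size per exit, from the plan's own numbers.** Inputs from Section 11: 18 per group needed, 20% drop-out, 44 enrolled. Allocation is 1:1 (Section 9).

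- Plan's enrollment: 2 × 18 = 36; 36 × 1.2 = 43.2, rounded up to 44. (Dividing gives 36 / 0.8 = 45.)
- Per arm: 44 / 2 = 22. One exit without later data: 1 / 22 = 4.5% of the arm.
- Allowed losses: 44 − 36 = 8, or 22 − 18 = 4 per arm. One exit uses 1 of those 4.

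**4. Why the bias cannot be sized.** Let k of 22 patients in an arm exit, and let e be their mean month-6 HbA1c minus that of the completers. Then the full-arm mean minus the completer mean is (k / 22) × e. The documents give neither k nor e, so these values are assumptions:

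- k = 1, e = +0.5: 0.02 points.
- k = 4, e = +2.0: 0.36 points.
- k = 4, e = −1.0: −0.18 points.

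A positive e would fit hyperglycemia exits and a negative e hypoglycemia exits. Across these assumed inputs the shift runs from negligible to a large part of the 0.5 margin, and the sign changes.

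**5. A caution about the remedy.** This step does not measure the present flaw. If k BI patients converted to MSI would otherwise be typical of their arm and reach the MSI mean (both assumptions, the first doubtful because they exit for extreme glucose), the as-randomized difference shrinks to (1 − k / 22) of its true value. The reduction is 4.5% for k = 1 and 4 / 22 = 18.2% for k = 4. This is why post-switch data need a supportive analysis.

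**The case against.** The best reply is that the plan is silent rather than wrong. It says all patients are followed for 6 months, HbA1c is timed from enrollment and not from treatment, and Section 13 never says that patients leave the study. Pregnancy follow-up is a safety provision and weak evidence about the other exits. Part of this stands: for the hyperglycemia exits and for every MSI exit, study withdrawal is inferred. It does not rescue the BI hypoglycemia rule, which names the study. The general follow-up sentence does not address withdrawn patients.

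A second reply is that the severe-hypoglycemia endpoint is hardly touched. That also stands. The trigger is narrower than the endpoint, because it requires two prior dose adjustments. A reader might infer that the first severe event ends follow-up, or that the incidence endpoints are lost; the documents support neither.

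A third reply concerns direction. A reader might infer that the rule favours BI because Section 14 warns that a large morning glargine dose may raise hypoglycemia risk. That is a risk disclosure, not a forecast. Section 3 sets out to show less hypoglycemia on BI, Section 5 excludes hypoglycemia unawareness, and Section 9 lowers the BI dose after any BG below 70 mg/dl or hypoglycemic symptoms. The documents do not settle which arm would lose more patients.

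Finally, 1 of 22 describes any drop-out, and the plan budgets for 20%. True: the figure measures data lost per exit, not bias.

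**Conclusion.** The point holds in limited form. Section 14 takes BI patients out of the study after severe hypoglycemia that persists through two adjustments. Section 13 probably does the same in both arms for that event and for the two hyperglycemia criteria, but does not say so. No provision exists for HbA1c or BG afterwards. Followed as written, the plan loses primary-endpoint values for reasons related to glucose control, and its analysis section has no rule for handling that.

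The documented size is 4.5% of an arm's month-6 HbA1c data, and 1 of 4 allowed losses, per exit. With no exit rates in the documents, the total size, the direction and the balance between arms remain unknown. It would go too far to say that the plan forbids all follow-up after every exit, or that it biases the trial toward non-inferiority. This is a worthwhile, inexpensive correction and not a demonstrated bias.

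**What to change.** In Sections 13 and 14, for all non-pregnancy criteria in both arms:

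- Replace study withdrawal with discontinuation or modification of the assigned regimen. BI patients convert to MSI as planned; MSI patients move to therapy chosen by the clinician.
- Continue Section 12 BG reporting and scheduled HbA1c to month 6 unless the patient withdraws consent. Record the date and reason for the change.
- In Section 11, report month-6 HbA1c and the secondary outcomes as randomized. Add a supportive analysis that does not use post-switch data, for example up to the regimen change, and say how a missing month-6 value is handled. Both are needed: BI patients converted to MSI can pull the arms together and favour non-inferiority, while dropping their later data brings back outcome-related missingness. Patients switched under the 3-month HbA1c rule belong in the same scheme.

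The cost is revised wording, a few more data reviews and one extra analysis. Section 25 treats testing supplies as standard care, so no new procedure is required, and the safety conversion is unchanged.

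Recruitment was due to end on 8/31/2022 and the document is dated 06/14/2023, so prospective collection may be over. In that case, report exits by arm and reason, and run both analyses on whatever later data the clinics hold.

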Effect of simplified insulin regimen on glycemic control and quality of life in an elderly population with type 2 diabetes

06/14/2023
NCT03660553

1) Protocol Title

Effect of simplified insulin regimen on glycemic control and quality of life in an elderly population with type 2 diabetes

2) IRB Review History*

Not applicable, the protocol has not been submitted for review by an external IRB.

3) Objectives*

Primary objective of this study is to test the hypothesis that once daily basal insulin (BI) is non-inferior to multiple subcutaneous injections (MSI) of insulin for glycemic control (HbA1c) in elderly patients with T2DM. A secondary aim of this study is to test that BI is superior to MSI for lowering HbA1c and is associated with lower incidence of hypoglycemia.

4) Background*

The prevalence of type 2 diabetes mellitus (T2DM) has been increasing over time, especially in the older age groups. According to the latest CDC data, 25.2% of the US population >65 years old has diabetes and it is expected to grow due to increase in life span as well as increase in incidence of T2DM [1, 2]. Many patients in this age group have other co-morbidities like heart disease, renal insufficiency, cognitive impairment, and lack of social support among others [3]. Elderly patients with T2DM are at an increased risk of hypoglycemia. Moreover, the benefits of tight glycemic control have not been established in this age group. Taking these factors into consideration, many professional organizations (American Diabetes Association, American Geriatrics Society) recommend relaxed glycemic goals (HbA1c ~8%) in the elderly population [4]. However, even for these relatively relaxed glycemic goals, insulin treatment is often necessary because due to associated comorbidities, many patients in this age group are poor candidates for non-insulin antidiabetic agents

[5]. Moreover, elderly patients with long standing T2DM may have decreased beta cell function and respond poorly to non-insulin antidiabetic agents [5].

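### BI patients whose HbA1c has not fallen within 3 months are moved to the comparator, and the primary analysis does not say how they count, so a true BI deficit can look smaller against the 0.5 margin

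*Combined protocol and SAP*

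**What the plan says.** Section 3 states the primary hypothesis as a comparison of regimens: "once daily basal insulin (BI) is non-inferior to multiple subcutaneous injections (MSI) of insulin for glycemic control (HbA1c) in elderly patients with T2DM". Section 8 sets the outcome: "Primary endpoint: Hemoglobin A1c (HbA1c) at 6 months after enrollment". Section 12 schedules HbA1c at randomisation and every 3 months, so a month-3 value is planned in both arms.

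Section 14 sends BI patients to MSI by two routes.

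- **No HbA1c response.** Patients without an HbA1c below baseline "within first 3 months of the study will be withdrawn from the BI group and placed on MSI regimen". No equivalent rule exists for MSI, and Section 13 does not list this one.
- **Severe hypoglycemia after two dose adjustments.** The patient leaves the study and is converted to MSI. The withdrawal itself applies to both arms, because Section 13 lists without regard to arm: "Patient with severe hypoglycemia needing assistance or BG below 54 ng/dl after two insulin dose adjustments". Only the conversion to MSI is specific to BI.

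Section 11 gives the main analysis as "an independent sample t-test or an analysis of covariance to allow for the inclusion of possible covariates such as age, baseline A1C". It reads the 95% two-sided interval "for the difference between BI and MSI treatment will be used for interpreting the results with regard to the non-inferiority margin". It names no analysis set, no rule for switched or withdrawn patients and no method for missing values. Treatment failure appears as a secondary outcome, without a definition or a link to the primary analysis.

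Study Timelines, under Section 7, adds: "All patients will be followed for a period of 6 month".

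**The concern.** A BI patient switched at month 3 can spend the second half of the trial on the comparator before the primary endpoint is measured. Section 14 itself foresees looser glycemic control on BI. If that happens and switched patients improve on MSI, their 6-month values pull the BI mean towards the MSI mean. In a superiority trial this would be conservative; here it favours the claim under test. BI could be declared non-inferior partly because its failures received the other treatment.

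The question being answered also changes. Scoring switched patients as randomised is a valid comparison of a strategy (start BI, move to MSI if it fails) with MSI. Section 3 and the interval in Section 11 are worded as BI against MSI. With no handling stated, the choice among several defensible options stays open until the data are in hand, and those options can fall on different sides of the margin.

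**Working it through.** **Inputs from the documents.** Margin 0.5, SD 0.9, 18 evaluable per group, two-sided 95% interval (Section 11). **Not in the documents, so assumed:** the share of BI switched (f), baseline HbA1c, correlations between visits, and how far switched patients recover on MSI.

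**Step 1, the plan's own figure.** The standard error of the difference is 0.9 × √(2/18) = 0.30. With no true difference, the noncentral t distribution (34 df) gives a power of 37%, not the stated 95%; 95% power would need 86 per group. This is a separate problem. The point here does not rest on it, but 18 per group and SE 0.30 are used below because they are the plan's figures.

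**Step 2, dilution.** Set the true BI deficit at the margin, 0.5, so that a correct test declares non-inferiority 2.5% of the time. Suppose post-switch values are scored in the BI group and switched patients reach MSI-level control. Then

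apparent deficit = 0.5 × (1 − f).

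Non-inferiority is declared when the estimate plus 2.032 × SE is below 0.5. Its probability comes from the noncentral t with noncentrality (apparent deficit − 0.5)/0.30.

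| f | Apparent deficit | Noncentrality | False non-inferiority, 18 per group | Same, 22 per group |
|---|---|---|---|---|
| 0% | 0.50 | 0 | 2.5% | 2.5% |
| 10% | 0.45 | −0.17 | 3.6% | 3.8% |
| 20% | 0.40 | −0.33 | 5.1% | 5.5% |
| 30% | 0.35 | −0.50 | 7.0% | 7.8% |
| 40% | 0.30 | −0.67 | 9.5% | 10.8% |

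The last column applies if all 44 enrolled are analysed. With half recovery the deficit is 0.5 × (1 − f/2). At f = 30% that is 0.425, with false non-inferiority of 4.3%. If the regimens are truly equal, the switch changes nothing and there is no shift.

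**Step 3, what share might switch.** Simulated trials applied the rule directly (switch if month-3 HbA1c is at or above baseline), with a true deficit of 0.5 and full recovery.

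- With an assumed baseline mean of 9.0 to 9.5 and two assumed correlation patterns, 11% to 30% of BI switch. False non-inferiority is 3.6% to 7.0% with the t-test and 3.9% to 8.1% with ANCOVA on baseline.
- If HbA1c at month 3 is still 0.4 above its month-6 level, under one of those patterns 26% to 46% switch and the t-test error is 6.2% to 11.0%.

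These are illustrations, not bounds.

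**Step 4, other handling.** A further simulation (18 per group, true deficit 0.5, assumed baseline mean 8.5 to 9.5, several correlation patterns, BI effect either constant or varying between patients) compared four ways of counting switched patients.

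| Handling | Apparent deficit | False non-inferiority |
|---|---|---|
| As randomised, post-switch value | 0.14–0.46 | 3.5–21% |
| Switched patients excluded | 0.07–0.50 | 2.4–20% |
| Counted as treated | 0.00–0.50 | 2.4–29% |
| Month-3 on-BI value carried forward | 0.52–0.68 | 0.5–2.4% |

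Exclusion and as-treated counting are unbiased only when the month-3 change is unrelated to the month-6 value and the BI effect is the same in every patient. Carrying the month-3 value forward enlarges the deficit.

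**Step 5, can imputation recover the BI effect?** Multiple imputation from arm, baseline and month-3 HbA1c returns 0.49 to 0.51 for a true 0.50 when the data follow the imputation model. It does not when they depart from it. With the deficit concentrated in 40% of patients (0.4 × 1.25 = 0.50), it returned 0.45. With a deficit of 0.85 in the roughly 30% who switch and 0.35 in the rest (0.3 × 0.85 + 0.7 × 0.35 = 0.50), it returned 0.35, the same as the uncorrected analysis at f = 30%. Every BI patient meeting the rule is switched, so no on-BI 6-month value exists to check the model there.

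**The case against.** The strongest reply has four parts.

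- **The rule is part of the BI arm.** The protocol manages BI as a strategy (Section 9 also splits large doses), so the as-randomised result answers a legitimate question. This stands as a defence of that analysis. It does not license the wording of Section 3, which concerns once-daily BI, and the plan nowhere says that the strategy is the target.
- **The handling may not be the one that shrinks the deficit.** The neighbouring hypoglycemia sentence pairs conversion to MSI with leaving the study, and 44 enrolled for 36 evaluable suggests that drop-outs are not analysed. If HbA1c switchers count as drop-outs, the table in Step 2 does not apply. This stands in part. Leaving the BI group, together with six months of follow-up for all, more naturally means that switched patients stay in the study, but the text does not settle it.
- **The size rests on assumptions.** This stands. The documents give no switch share, baseline HbA1c, correlations or recovery, and the error rates put the true deficit exactly at the margin.
- **Imputation is no cure.** This stands, for the reason shown in Step 5, so no single imputation model should carry the claim.

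A reader might infer that a BI deficit will necessarily look smaller. The documents do not support that: the direction depends on the unstated handling and on recovery after the switch. Nor are HbA1c non-responders the only BI patients who go to MSI.

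**Conclusion.** The concern holds in conditional form. The 3-month HbA1c rule applies to BI only, its destination is the comparator, and the primary analysis states neither an analysis set nor how switched patients count. If their post-switch values are scored in the BI group and they improve on MSI, a true deficit can look smaller and non-inferiority can be declared too often. With a true deficit of 0.5 and full recovery, the error is roughly 1.4 times nominal at 10% switched (3.6/2.5) and 3.8 times at 40% (9.5/2.5). Partial recovery reduces it; a BI effect that varies between patients can increase it.

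The one-sided rule and the missing handling are certain from the text. The size is not. It would be an over-reading to say that the trial's result is biased: with equal regimens, as-randomised scoring causes no shift. The omission still bears directly on the primary conclusion and should be corrected, because the plan leaves open whether that conclusion concerns BI or BI with rescue by the comparator.

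**What to change.** 1. Analyse all randomised patients in their assigned group using the 6-month HbA1c, including those switched or withdrawn. Impute values that were not collected rather than exclude the patient, and report how many.
2. State that this result compares starting BI and moving to MSI if it fails with MSI. Limit the non-inferiority conclusion to that unless the analyses in item 3 agree.
3. Add sensitivity analyses that do not use post-switch HbA1c: multiple imputation from arm, baseline and month-3 values, plus at least one less favourable to BI, such as the month-3 on-BI value carried forward or a delta-adjusted imputation.
4. Report by arm the number meeting the 3-month HbA1c criterion and the number switched.
5. Reconcile Sections 13 and 14 on whether a switched patient leaves the BI regimen or the study. The clinical rule itself is for the investigators.

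**Timing.** Recruitment was planned to 8/31/2022, so six-month visits would have ended about February 2023. This version is dated 06/14/2023, and Study Timelines says: "The estimated date to complete the primary analysis will be 06/2023". If that schedule held, uncollected values can only be imputed. If the primary analysis has already been run, the analyses in item 3 must be labelled post hoc.

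**Cost.** Plan wording, one or two extra analyses, and a somewhat lower chance of supporting non-inferiority for BI alone. With no true difference and 18 per group, simulated power of the multiple-imputation analysis is 34% to 37%, or 31% to 36% with the assumed month-3 lag of 0.4, against about 37% without switching. The analysis less favourable to BI makes agreement harder still.
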